### 4.2 Exclusion Criteria

Patients ineligible for participation include:

1. Major congenital malformations and/or intrauterine growth retardation, defined as birth weight  $<2000$  gm
2. Medical illness requiring intensification of medical therapy. This includes but is not limited to suspected sepsis requiring antibiotic therapy.
3. Hypoglycemia requiring treatment with intravenous dextrose
4. Bilirubin  $>20$  mg/dL (The need for phototherapy is not exclusionary)
5. Inability of mother to give informed consent due to co-morbid psychiatric diagnosis

### 4.3 Patient Baseline and Allocation Numbers

All patients for whom consent is obtained will be given a four-digit baseline screening number that begins with sequence 4001. Patients who require treatment and are allocated to will receive a three-digit allocation number that begins with sequence 501.

## 5 DRUG ADMINISTRATION REGIMEN

### 5.1 Identity

All study drug will be prepared in bulk solution, distributed to the patient ward, and unit dosed by nursing in 1 mL pediatric dispensing vials (Healthcare Logistics Cat. # 7870 or equivalent). Preparation and stability is listed in Appendix 2.

## 5.2 Calculation of Dose and Administration

### 5.2.1 *Buprenorphine*

Buprenorphine solution will consist of simple syrup, ethanol 30% final volume, and buprenorphine. The final concentration of buprenorphine is 0.075 mg/mL total volume. The patient weight at the initiation of dosing will be used for the calculation of all subsequent doses of buprenorphine. The calculation of maximum dose will be based upon weight at time of administration. Dose will be communicated with the primary team by way of a dose sheet. The primary team will order the buprenorphine using the electronic medical record. This includes protocol specified maximum of 75 mcg/kg/day for buprenorphine. To allow for alterations in sleeping and feeding schedules, each dose of buprenorphine can be administered +/- 30 minutes around the nominal time point for that dose. Actual time that each dose was administered must be recorded in the medical record. The study drug administrator will hold the child's head at approximately 45 degrees, gently move the tongue to the side, administer the drug under the tongue, and immediately place a pacifier in the mouth to reduce swallowing of drug. If the volume of the drug is >0.5 ml, half of the drug will be administered, followed by the remainder of the dose in approximately 2 minutes.

#### 5.2.1.1 *Starting doses*

The starting daily dose for buprenorphine will be 24 mcg/kg/day (8 mcg/kg/q8 hours).

#### 5.2.1.2 *Cessation dose*

The cessation dose will be ≤ initiation dose.

### 5.2.2 *Phenobarbital*

The hospital standard of care phenobarbital elixir formulation (20 mg/5 ml or similar equivalent) will be used. Birth weight will be used for the calculation of phenobarbital loading and maintenance dose. A loading dose 20 mg/kg followed by daily oral dose of 5 mg/kg/day will be used. When buprenorphine is weaned to 50% of highest dose, phenobarbital is decreased to 2.5 mg/kg/day. After three additional opioid weans, phenobarbital will be discontinued and the buprenorphine weaned until cessation dose was met.

## 5.3 Drug Product Quality Control

### 5.3.1 *Drug Preparation Procedures*

Preparation of stock solution for study drug will take place in the pharmacy of Thomas Jefferson University Hospital.

### 5.3.2 *Stability*

Buprenorphine solution will be used within 30 days of stock drug preparation. Buprenorphine has stability in plastic syringes for at least 7 days at room temperature.

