## APPENDIX 2: PREPARATION OF BUPRENORPHINE STOCK SOLUTION AND STABILITY

	Stability of Stock

Buprenorphine 0.075 mg/mL
 
Composition of neonatal stock solution
 

• One 0.3 mg ampule buprenorphine [Buprenex 0.3 mg/ 1 ml (Reckitt Benckiser) or generic buprenorphine for injection]

• Ethanol to bring to final concentration of 30% (1.26 mL of 95% ethanol USP)

• Simple syrup USP(Sucrose, Purified Water and 0.1% Sodium Benzoate) to bring to 4 mL total volume [Humco or equivalent]

 
0.3 mg buprenorphine per vial * 4 mL  (final volume) = 0.075 mg/mL
	7 days

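### Section 5.3.2 allows the buprenorphine solution to be used for 30 days after stock preparation, but Appendix 2 lists 7 days of stock stability for the same 0.075 mg/mL solution

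*Protocol*

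**What the plan says.** Four parts of the protocol bear on this point.

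- **Section 5.3.2 (Stability)** sets a limit on use: "Buprenorphine solution will be used within 30 days of stock drug preparation". A second sentence gives a different figure for a different container: no less than 7 days in plastic syringes at room temperature, with a citation to a published formulation study (reference 37).
- **Section 5.1 (Identity)** makes the appendix the place to look: "Preparation and stability is listed in Appendix 2". It also describes how the drug is handled. It is made up in bulk, then "distributed to the patient ward, and unit dosed by nursing in 1 mL pediatric dispensing vials".
- **Appendix 2** has two columns. The first, under "Composition of neonatal stock solution", gives the recipe and ends with the concentration: "final volume) = 0.075 mg/mL". The second is headed "Stability of Stock" and holds a single entry, 7 days. It names no container, temperature or source.
- **Section 5.2.1** describes one buprenorphine solution: "The final concentration of buprenorphine is 0.075 mg/mL total volume". The synopsis describes the same product.

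Section 5.3.1 adds who makes it: "Preparation of stock solution for study drug will take place in the pharmacy".

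**The concern.** The section titled Stability and the appendix designated for stability give different figures for the stock, 30 days and 7 days. Both are tied explicitly to the stock: section 5.3.2 counts from the day it is prepared, and the appendix puts the word in its column heading.

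This is a working instruction. Pharmacy makes the stock, and ward nurses draw unit doses from it. Someone holding a bottle from day 8 to day 30 after preparation finds it within the permitted period in section 5.3.2 and beyond its listed stability in Appendix 2. Two people following the same protocol could act differently and both believe they are compliant.

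The link to the analysis is modest. The primary endpoint (section 3.2.1) compares the exposure profile of the new regimen, estimated by population pharmacokinetics, with model simulations. Such a model takes recorded doses as given. A shortfall in delivered drug, if one occurred, would look like a difference in exposure or clearance, and with 10 infants it would be hard to separate from true variability. The protocol gives no evidence of such a shortfall. It should nevertheless state one limit that is clearly tied to the stability data.

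**Working it through.** No sample size, power or error rate is involved. The check is whether the two figures describe the same thing, and how far apart they are.

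**Step 1. Is it the same product?**

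| Item | Appendix 2 | Section 5.2.1 |
|---|---|---|
| Buprenorphine | 0.3 mg / 4 mL = 0.075 mg/mL | 0.075 mg/mL |
| Ethanol | 1.26 mL × 95% / 4 mL = 29.9% | 30% |
| Vehicle | simple syrup | simple syrup |

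The products match. The protocol describes no second formulation to which either figure could belong.

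**Step 2. Is it the same quantity?**

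| Source | Figure | What it is attached to |
|---|---|---|
| Section 5.3.2, first sentence | 30 days | use of the solution, counted from stock preparation |
| Section 5.3.2, second sentence | at least 7 days | plastic syringes, room temperature |
| Appendix 2 | 7 days | stability of the stock |

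The second row does not conflict with the first, because it gives a minimum for a different container. The conflict is between the first row and the third.

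**Step 3. How large is the gap?**

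- Difference: 30 − 7 = 23 days, that is, days 8 to 30 after preparation.
- Ratio: 30 / 7 = 4.29.

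**Step 4. Could stock reach day 8?** The protocol fixes no batch size. As an illustration, take a single 4 mL preparation and the starting dose of 8 mcg/kg. The infant weights are assumptions.

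| Assumed weight | Volume per dose (8 mcg/kg × weight ÷ 75 mcg/mL) | Whole doses in 4 mL | Lasts at q8h | Lasts at q24h |
|---|---|---|---|---|
| 2 kg | 16 / 75 = 0.213 mL | 18 | 6 days | 18 days |
| 3 kg | 24 / 75 = 0.32 mL | 12 | 4 days | 12 days |
| 4 kg | 32 / 75 = 0.427 mL | 9 | 3 days | 9 days |

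A single preparation for one infant would usually be used up before day 8 at the 8-hourly interval, but not at the 24-hourly interval that ends the wean. Section 5.1 speaks of bulk preparation, which could be larger than 4 mL. The disputed window can therefore be reached in practice.

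**Step 5. Does anything else reconcile the figures?** No. No section distinguishes them by temperature, by container, or as a tested duration against a use-by date. The table of protocol versions records no change to stability, so neither figure is marked as superseded.

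**The case against.** The strongest counter-argument is that there is no real conflict, only a mislabelled cell. Section 5.3.2 itself separates a stock-use period (30 days) from a container-specific figure (at least 7 days in syringes), and the 7 days in Appendix 2 matches the latter. On that reading the appendix has carried over the syringe figure. This is plausible, but the column heading refers to the stock, the appendix mentions no syringe, and nothing confirms the carry-over. If the reading is correct, the appendix is wrong as labelled and still has to be changed. Nor would the syringe figure clearly cover the ward doses, which section 5.1 puts in dispensing vials.

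A second argument is that the passages can both be obeyed: stock used by day 7 satisfies each, and Appendix 2 contains no instruction to discard. This is true and narrows the claim, since a stability entry is not literally a use limit. It still leaves a permitted period more than four times the listed stability of the same solution, without explanation.

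A third is that the matter is slight: a pharmacy inconsistency in a small descriptive study, with no demonstrated effect on dose or exposure. It is fair that no such effect can be derived from the protocol, and that the point has no bearing on power or error rates. This limits the weight of the finding but does not remove the contradiction.

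Loss of a qualifier when the appendix table was converted from PDF cannot be wholly excluded, but the heading and entry are both legible and nothing suggests missing text.

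**Conclusion.** The concern holds. The protocol gives two irreconcilable figures for the same stock solution, 30 days for use and 7 days for stability, which leaves a window of 23 days (a ratio of about 4.3) in which its instructions disagree. It should be corrected.

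Confidence is high, but only in the mismatch. That part rests on the text and on the arithmetic showing that both passages describe the 0.075 mg/mL, 30% ethanol solution. No loss of potency and no effect on exposure is claimed or estimated. The protocol does not show which figure is correct, and the formulation study it cites was not available for this review. The infant weights used to show that stock could reach day 8 are assumptions, and the mismatch does not depend on them.

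**What to change.** Reconcile section 5.3.2 and Appendix 2 so that both state the same in-use period for the stock, with its storage condition and the stability data that support it. If unit-dosed containers have a different period, state it separately and name the container, bearing in mind that section 5.1 refers to dispensing vials and section 5.3.2 to syringes. If the 7 days in Appendix 2 is the syringe figure, relabel it as such. The choice of period belongs to the sponsor and the pharmacy on the basis of those data.

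The cost is a wording correction in one or both places. Depending on the period the data support, stock may have to be prepared more often.

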### 5.3.3 *Investigational New Drug (IND) Certification*

This protocol is being conducted under existing IND # 68,403

## 6 STUDY PROCEDURES

### 6.1 Identification of Potential Study Subjects

Potential subjects will be identified through the outpatient treatment clinics and by review of all infants at risk for NAS based on maternally identified use of opioid therapy. All infants at risk for NAS have standard care NAS scoring conducted every 4 hours. Consented infants with the sum of three scores  $\geq 24$  or more or a single score of  $\geq 12$  will be eligible for allocation. The ultimate decision to initiate treatment will be that of the treating pediatrician. A child will be allocated only after a definite decision to treat is made. All infants who have genetic consent obtained will have a blood sample for DNA analysis obtained, ideally at the time of a clinically indicated draw.

Infants not meeting the treatment threshold criteria will be observed at least 3 days postpartum in an inpatient setting prior to discharge. Infants who have the sum of three scores  $\geq 18$  but  $< 24$  can be observed additional days as inpatients at the discretion of the attending physician.

### 6.2 NAS Scoring Procedures

NAS scoring for each subject will take place at 4 hour intervals (+/- 30 minutes to account for sleeping and feeding schedule). The exact time of scoring will be recorded in the medical record.

### **6.4 Dose Escalation**

Dose escalation of 33% of the previous dose will take place if

- the sum of 3 NAS scores is  $>24$  or a single score is  $>12$   
OR
- a rescue dose was administered [section 6.5].

To mimic actual clinical care, dose advancement will generally take place in daylight hours when the primary team caring for the patient is present. However, dose advancement may take place when the primary team is not present (such as would occur on evenings and nights). All dose decisions will be made based on the three most recent scores. No more than one dose escalation can take place each day, unless there is need for an additional rescue dose post-escalation.

### **6.5 Rescue Dose**

If, between scheduled doses, a child has a single score of  $\geq 12$ , a rescue dose may be administered at the discretion of the treating physician. The rescue dose will be same as the previous dose. A rescue dose must be given at least 1 hour after and 1 hour before the next scheduled dose.

### **6.6 Weaning**

The initiation of weaning can take place as soon there are 48 hours of stability without dose advancement.

- Doses will be weaned when the sum of the previous three scores is  $<18$  and no single score is  $\geq 8$ .
- Dose reductions will occur at a rate of 15% per wean until reaching the bottom dose ( $\leq$  initial dose).
- After bottom dose is reached, next weaning step is from q8 to q12 hours, followed by a step from

q12 to q24 hours.

- If the sum of the previous three scores is  $\geq 28$  and at the discretion of the treating physician, the standing dose will revert to the previous dose or dose interval at which symptoms were controlled.

Weaning is expected to take place during daylight hours when the primary team is present, but dose adjustments can take place on evenings and nights. Only one wean of dose will take place each day. A rescue dose may be administered at the discretion of the treating physician during the weaning period if a single score  $\geq 12$ . A rescue dose during the wean will be the same as the previous dose. The administration of a rescue dose in the weaning period will not trigger a dose escalation.

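### Sections 6.4 and 6.6 prescribe different dose actions for the same scores in a weaning infant, and the protocol text does not say which section governs

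*Protocol*

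**What the plan says.** Section 6.4 opens with "Dose escalation of 33% of the previous dose will take place if" and lists the triggers: a three-score sum above 24, a single score above 12, or administration of a rescue dose. It names no treatment phase and adds "All dose decisions will be made based on the three most recent scores". Section 3.1 has a similar advancement rule, with a sum of 24 or more and neonatologist discretion, again with no phase named.

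Section 6.6 covers weaning. A wean requires a three-score sum below 18 and no single score of 8 or more. On step size it says "Dose reductions will occur at a rate of 15% per wean until reaching the bottom dose", after which the interval is lengthened to 12 and then 24 hours. For worsening symptoms, once three scores total 28 or more, the physician in charge may decide on a reversion, worded as "the standing dose will revert to the previous dose or dose interval at which symptoms were controlled". A rescue dose is optional after a single score of 12 or more, and "The administration of a rescue dose in the weaning period will not trigger a dose escalation".

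**The concern.** Any sum that meets the 6.6 reversion threshold also meets the 6.4 escalation threshold, and the two actions differ. Sums of 25 to 27, and single scores above 12, meet the 6.4 threshold but lead to no change of standing dose under 6.6. Section 6.6 withdraws one 6.4 trigger for the weaning period, the rescue dose, and does not mention the score triggers. A reader can fairly conclude that the score triggers still apply.

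Two things are at stake. The conflict bears directly on the dose an infant receives. The pharmacokinetic endpoint in Section 3.2.1 also compares the exposure profile of the revised dose schema with model simulations. If the schema has two readings during weaning, the observed courses do not represent one defined regimen, and with 10 infants a few divergent decisions could be visible in exposure and in the exploratory length of treatment.

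**Working it through.** **Inputs.** Escalation: +33% of the previous dose, at a sum >24 or a single score >12 (6.4). Reversion: sum ≥28, discretionary (6.6). Wean: 15% per step, so a factor of 0.85 (6.6). Maximum unit dose: 25 mcg/kg (6.8).

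**Check of the 33% rule against Table 5.** Starting from 8 mcg/kg and multiplying by 1.33 each time gives 10.64, 14.15, 18.82 and 25.03. Table 5 gives 10.6, 14.2, 18.8 and 25.0. The figures agree to within 0.4%, so 33% means multiplying the previous dose by 1.33.

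**The two sections side by side, for an infant already weaning:**

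| Last three scores | 6.4 read literally | 6.6 |
|---|---|---|
| Sum 25–27, e.g. 9+9+9 = 27 | +33% | neither wean nor reversion: dose held |
| Sum ≥28, e.g. 9+9+10 = 28 | +33% | discretionary reversion |
| Single score >12, low sum, e.g. 13+4+4 = 21 | +33% | optional rescue, no escalation |
| Sum 24, no score >12, e.g. 8+8+8 | no action | dose held |

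The first three rows conflict. In the last row both sections leave the dose unchanged.

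**The rescue exception.** A rescue needs a score of at least 12, and under 6.4 any score above 12 escalates by itself. If the score triggers stay in force and the sum is not above 24, the exception changes the outcome only for a highest score of exactly 12.

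**Size of a reversion, to set against +33%:**

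- One wean step undone: 1/0.85 = 1.176, or +17.6%.
- Two steps: 1/0.85² = 1.384, or +38.4%.
- Three steps: 1/0.85³ = 1.628, or +62.8%.
- Interval from 12 back to 8 hours at the same unit dose: 3/2 doses per day, or +50% daily dose.
- Interval from 24 back to 12 hours: 2/1 doses per day, or +100% daily dose.

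During the interval steps the two sections also act on different quantities: 6.4 raises the unit dose, while 6.6 restores the interval.

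**Example.** A dose of 14.2 mcg/kg weaned once is 14.2 × 0.85 = 12.07. Escalation under 6.4 gives 12.07 × 1.33 = 16.05, above the earlier peak. A one-step reversion under 6.6 gives 14.2.

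**At the cap.** With weight unchanged, one wean from 25 gives 21.25. Then 21.25 × 1.33 = 28.26, which the cap limits to 25, so escalation and a one-step reversion both come to +17.6%.

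**The case against.** The strongest reply is that the sections govern successive phases: 6.4 the period before weaning, 6.6 weaning itself. Section 3.1 describes that order. Every sum of 28 or more is also above 24, so applying 6.4 throughout would leave the reversion rule without effect. Yet version 1.1 deliberately edited that rule to add the dose interval. Under phase separation, 6.6 covers all scores, and its rescue sentence is an ordinary clarification, since rescue is allowed in both phases. The algorithm figures are not shown and may draw the separation.

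Much of this stands, and phase separation is the more coherent reading. It remains an inference: 6.4 has no limiting words, and the rescue sentence, by switching off one trigger alone, also supports the opposite inference. The unseen figures support neither side.

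The effect on the primary analysis is also limited. Actual administration times are recorded (Sections 5.2.1 and 6.3), so PK estimation can use the real dosing history. Length of treatment is exploratory, and physician discretion is built in.

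Two stronger claims that a reader might infer are not supported:

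- *A milder score triggers a larger increase than a worse one.* This requires 6.4 to govern sums of 25 to 27 while 6.6 governs 28 and above, a hybrid the text does not state. It also requires a one-step dose reversion away from the cap. Either section applied throughout produces no such inversion, and reversions of two or more steps or of an interval exceed 33%.
- *Each event costs about four extra treatment days.* Undoing +33% takes ln(1.33)/−ln(0.85) = 1.75, so two, daily weans. The other two days assume that the 48-hour stability period restarts, but 6.6 attaches it to the start of weaning. Holding or reverting costs days as well, so four days is not a difference between readings.

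**Conclusion.** The point holds as a conflict in the text. For a weaning infant with a sum of 25 to 27, the next dose is unchanged or 33% higher, depending on the section followed. With a sum of 28 or more, it is 33% higher or a discretionary reversion: +17.6% for one undone step, more for several steps or an interval. With a single score above 12 and a low sum, it is 33% higher or unchanged with an optional rescue.

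These figures assume that 6.4 is read literally and, for the +33%, that the cap does not bind. The protocol gives no frequency for such scores during weaning, so the total effect cannot be estimated. What is affected is consistency of dosing in 10 infants and the definition of the regimen compared with simulations. The validity of PK estimation from recorded dose times is not in question, and no sample size or error rate is involved. The point should be corrected because it bears on an infant's dose and is simple to resolve.

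**What to change.** Reconcile Sections 6.4, 6.6 and 3.1 by stating which section governs once weaning has begun. State this separately for sums of 25 to 27, sums of 28 or more, and single scores above 12, and cover the interval steps at the bottom dose. Check that the study algorithm figures show the same rule, and use it in the simulations with which the observed exposure is compared. Which rule is right is a clinical decision for the sponsor and investigators, and this review takes no position on it. The cost is a short protocol clarification, with no extra data or visits.

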## **6.7 Buprenorphine Dose Cessation and Observation**

The cessation dose of buprenorphine is at or below the initial dose. Following wean of interval at the bottom dose, buprenorphine dosing will cease. Infants will be observed in an inpatient setting for at least 2 days following last dose, during which time scoring of NAS symptoms will continue. A rescue dose after cessation of therapy may be given at the discretion of the treating physician for any score of  $\geq 12$ . The amount of drug administered will be the last dose the patient had received. If a post cessation rescue dose is given, patients must be observed at least 1 day following the last rescue dose.

